Development and Evaluation of a New Infant Nutrition Screening Tool (Infant Yorkhill Malnutrition Score)

Introduction

A large number of children experience undernutrition related to or resulting from their illness. Hospitalized children are at a high risk of developing malnutrition particularly children with underlying disease and clinical conditions (Joosten KF and Hulst JM, 2008, 2010). In addition malnutrition has been associated with an increase in length of hospital stay and consequently the cost of providing health care (Campanozzi A et al, 2009). Therefore, the identification of children at risk of undernutrition is an important part of any programme for providing optimal health and treating of hospitalized patients. Quality Improvement Scotland has recently published standards for Food Fluid and Nutritional Care, which state that all patients should be screened for undernutrition on admission and periodically during their stay at hospital (NHS QIS 2003).

Common methods of assessing nutritional status in children include a combination of dietary, anthropometric, biochemical measures and clinical signs. It is not possible for all admitted patients to have a complete nutritional assessment, but nutritional screening aims to identify those who are malnourished or at risk of becoming so to allow them to be assessed in more detail. In terms of anthropometric measures, the three most commonly used anthropometric indices are weight-for-height, height-for-age, and weight-for-age; According to WHO criteria, (WHO technical report, 1995) SD-scores<-2 for weight-for-height and height-for-age describe acute and chronic malnutrition respectively. BMI as a new indicator has been developed by WHO for the first time to assess (the thinness of a child and hence its probability to indicate malnutrition of children) the weight of children (De Onis M et al, 2006). Weight-for-height index has been suggested as valid criteria for the identification and treatment progress of severe acute malnutrition in children (Isanaka S et al, 2009). These indexes can be used for screening of chronic and acute malnutrition but their diagnostic value is limited when attempting to identify children at early stages of undernutrition or patients at risk of deterioration in nutritional status as the result of medical condition.

There is no agreement concerning the most appropriate criteria to be used. What is needed is a valid and accessible tool to establish the early identification and desirable management of nutritional risk in children. . There remains a great variation in the criteria used to define malnutrition, with each method having its own limitations.

Pre-existing paediatric nutrition screening tools

Recently a variety of nutritional screening tools have been developed for assessment of nutritional status of children in hospital setting, including; SGNA (Subjective Global Nutritional Assessment) (Secker and Jeejeebhoy, 2007), STAMP (Screening Tool for the Assessment of Malnutrition in Paediatric) (McCarthy H, et al. 2008 and More J, 2008),

STRONG kids (Screening Tool Risk on Nutritional Status and Growth) (Jessi M. Hulst et al., 2010), and PYMS (Paediatric Yourhill Malnutrition Score). These all use the internationally recognized predictors of undernutrition: clinical assessment, dietary intake and anthropometric measurements. Each of these components bears a nutrition risk score, and overall score corresponds to the overall undernutrition risk of the patient. Although, recent studies have attempted to develop appropriate nutritional screening tools for children on admission, they are not useful for infants as they have not been validated except of STRONG kids (Screening Too Risk on Nutritional Status and Growth) which has been developed for hospitalized children as well as infants.

Development of the infant Paediatric Yorkhill Malnutrition Score (iPYMS)

A project team, consisting of senior nursing, dietetic, research academic and medical staff have developed a preliminary tool that would be both simple and quick to use. The infant nutritional screening tool will consist of four fields;

1. Weight centile (using admission weight)
2. Poor weight gain (by parental report)
3. Reduced intake
4. Effect on nutrition of current illness

On admission this tool would be completed by the nurse (researcher initially). A score of 0 or 1 classify patient at a low and median risk of undernutrition and a score of 2 or more reflects a high risk of undernutrition.

Purpose of the Study

The purpose of this study is to evaluate a proposed malnutrition screening scheme for infants - the infant Paediatric Yorkhill Malnutrition Screening(iPYMS)score to discover how well it distinguishes infants who are well-nourished from those undernourished or at risk of undernutrition (discriminant validity).

We also need to compare it with results of other reputable nutritional measurements (concurrent validity).

Hypotheses

1. Most infants with low fat levels or at high risk of undernutrition with Paediatric Global Nutritional Assessment (PGNA) will be identified by a high infant Yorkhill Malnutrition Score (sensitivity).
2. Infants with high infant Yorkhill Malnutrition Score will have lower fat levels than infants with low score (discriminant validity).
3. There will be a moderate to good agreement and concordance between infants who have been screened with iPYMS and STRONG kids.
4. Explore the utility of bioelectrical impedance and an infant eating behaviour scale in detecting infants with malnutrition
5. Relate the malnutrition risk to length of hospital stay

Method

The researcher will pilot the study and this will be the opportunity receive feedback on the study design. The researcher will first complete the iPYMS scoring sheet for each

child and then the questionnaires (SGNA and Infant EBQ) will be completed by the main carer of patient.

The Paediatric Yorkhill Malnutrition Score (PYMS) for infants must be able to distinguish those who are well-nourished from those malnourished or at risk of becoming so. It is based on internationally recognized predictors or symptoms of undernutrition (weight gain, reduced dietary intake), and therefore has face validity. However we need to compare it with results of other reputable nutritional measurements (concurrent validity), and its diagnostic value to screen the same patients with other currently used methods of undernutrition has to be tested (criterion validity). Accuracy is also important, considering how well the tool performs in detecting infants who really have problems and correctly identifying those who do not (sensitivity and specificity). So, we need further measurements to consider its sensitivity and the discriminant validity of the tool. We will study all screen positive and a sample of screen negative infants, using skinfolds and previous weight measurements and a parentally completed eating behaviour questionnaire. We will use this data to test the utility of PYMS score, growth trajectory, body mass index and behaviour questionnaire as predictors of low adiposity and stunting.

The discriminant validity of the screening tool will be tested using body composition measurement using triceps (TSF) and subscapular skinfold thickness and the mid upper arm circumference (MUAC) and SGNA (Subjective Global Nutritional Assessment). To test the concurrent validity, the results from the infant screening tool will be compared with the results of STRONG kids (Screening Tool Risk on Nutritional Status and Grow).

Reliability is also essential as the tool must produce similar results with repeat testing in the same circumstances and with different users where the patient's state has not changed. User-group may affect tool performance; for example, whether doctors, nurses or dieticians conducted the screening. Thus, the reliability of the tool needs to be tested in future.

Subjects

Participant of the study will be all patients newly admitted to selected wards (medical and general surgical wards) at the Royal Hospital for Sick Children (and possibly RAH Paisley). An average of 8 patients per day are admitted to the relevant wards and we will aim to recruit a total of 200 over a 4 month period, after an initial pilot with up to 20 patients. Children aged 1 -24 months are the subjects of this study because the purpose of this study is to develop a screening tool for infants.

Exclusions

- Patients in the short stay ward, intensive care or high dependency unit, Oncology unit, NICI and PICM, Cardiology (SA),
- Patient who have been transferred from neonatal units and PICM and NICM.

Sample Size- Power Calculation

Using the Altman monogram 45 subjects in each group (135 in total) would give 90% power to detect a difference of 0.66SD (1 centile space) in skinfolds between any two of the 3 groups. 70 subjects in each group (210) gives 80% power to detect a difference of 0.5SD in skinfolds between any two of the 3 groups.

It is likely that not all children will have complete measures so we will aim to recruit 200 subjects.

Sample Selection

Quota sampling will be used to obtain three equal groups of patients with different undernutrition scores (low, medium, high), until the desirable number of patients in each group is achieved. We will oversample high risk patients (expected to be only 10-20% of all patients) if necessary by screening all eligible patients using iPYMS and proceeding to full assessment for only those scoring high risk. In other word. a) The majority of patients screened at high risk of undernutrition. b) Every third child screened at medium risk of undernutrition. c) Every tenth child screened at low risk of undernutrition (Gerasimidis K et al, 2010).

We expect that malnutrition will be identified in between 10-30% of infant studied. If previously unrecognised this means they can then be referred for further assessment.

Recruitment

The researcher will identify those patients eligible for screening by visiting the wards daily and obtaining details of new admissions from the nursing staff. She will then give an information leaflet to the patient's carer to read and answer any immediate questions. After at least one hour she will return to the ward and if the carer is happy to participate, the researcher will ask him/her to complete a consent form. A copy of the consent form will be given to the carers and another will be placed in the child's medical notes.

The material will be in written in a form suitable for anyone who can read English. We will not be able to include those infants where neither carer was able to read English.

Due to short admission periods usually most of the children will be discharged during the first day of stay. We aim to complete assessment on the next day after admission

Outcome Measurements

Parental questionnaires

1. Global Nutritional Assessment for infants (SGNA)

The researcher will ask the main carers of patients to complete the eating behavior questionnaire about the infant's diet (type of milk, supplementary feeding and weaning diet), weight loss (poor weight gain), gastrointestinal symptoms, and daily activity. A rough visual assessment of the child's muscle stores and fat will be carried out by the researcher. This is a global nutritional assessment procedure recently validated in paediatric patients as a measure of current and future nutrition risk (Secker & Jeejeebhoy, 2007). A copy of the assessment form and the article that describes this method is attached for the ethics committee attention.

2. Infant EBQ

This questionnaire has been developed using population data from a cohort study and is designed to identify infants at risk of weight faltering. This will be completed by the main carers of patients to assess the patient's general appetite and eating behaviour

Measurements

3. Triceps (TSF) and subscapular skinfold thickness

Measurement of the thickness of the skin of the arm (triceps) and shoulder blade (subscapular) will be done as a measure of fat store. Briefly the parent will take off their top clothing and the researcher will measure the skinfold thickness with Holtain calipers. This measurement will be to some extent inconvenient for patients particularly those who are <1 year of age.

4. Weight and length

Weight will have been measured on admission. The researcher will re weight and measure length using the ward scales and recumbents stadiometer or our own portable equipment.

5. Mid upper arm circumference (MUAC)

The researcher will measure the circumference of their mid upper arm using a simple measuring tape.

6. Bioelectrical impedance (BIA)

This has been developed for assessment of nutritional status in children based on indices of lean and fat adjusted for body size (Wright CM et al, 2008). We want to discover whether this method is practical and effective in this young age range and how it relates to nutrition score. Self adhesive electrodes are attached to the right wrist and ankle while the child lies on the bed. Three reading are taken, while, the electrodes are attached

The infants may become briefly upset by being measured. If they become very upset and uncooperative that measurement will be abandoned.

Additional elements

7. STRONG kids (Screening Tool Risk on Nutritional Status and Growth)

The researcher will extract equivalent items for SGNA about the child's food intake, diarrhoea, vomiting, weight loss or poor weight gain or no weight gain, during the few days before admission. An observational assessment of patients will be also carried out by researcher in terms of diminished subcutaneous fat, muscle mass and hollow face (subjective clinical assessment- the same as b). In addition, the researcher will use information recorded in the medical notes of the patient to assess patients' underlying illness with a risk of malnutrition (Anorexia nervosa, Celiac disease, Cystic fibrosis, cardiac disease, and trauma).

8. Length of hospital stay (LOS)

Length of hospital stay as a secondary outcome will also be collected from hospital admissions statistics or through the notes.

9. Growth trajectory

Patients' birth weight will be collected by the maternal report in order to calculate weight trajectory.

Analysis-Statistics

Data will be entered into the electronic database of SPSS v15. The paper data will have names and dates of birth recorded in order to allow linkage to hospital discharge data. The electronic data will have only enough personal information to link it uniquely with the paper record. The anonymised electronic data will be stored on the password protected university network.

The raw measurements of body composition, height, weight. Skinfolds and mid upper arm circumference will be converted into standard deviation scores.

- Height and weight will be converted into standard deviation scores according to the UK 1990 reference data.
- Skinfolds and mid upper arm circumference will be converted into standard deviation scores according to the World Health Organization reference values. A value less than -2 standard deviation scores denotes a patient at high risk of undernutrition.

Patient iPYMS outcome (nutrition risk), will be cross-tabulated with the respective nutrition risk from the Paediatric Subjective Global Nutrition Assessment or, body composition assessment. The proportion of patients at risk of undernutrition (according to body composition assessment and/or the Paediatric Subjective Global Nutrition Assessment) who were not identified by the iPYMS will be recorded as false negatives. On the contrary, the proportion of patients at low risk of undernutrition (according to body composition assessment and/or the Paediatric Subjective Global Nutrition Assessment) who were screened as at high risk of undernutrition by the iPYMS will be recorded as false positives.

The mean values per group compared using t-test and anova and the categorical data compared using chi squared and logistic regression analysis.

We will use this data to test the utility of PYMS score, growth trajectory, body mass index and behaviour questionnaire as predictors of low adiposity and stunting
K-statistics will be used for Agreement of the methods.

References

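### The protocol's selection rules for full assessment cannot all be followed, and the fixed fractions of one in three and one in ten do not reliably fill three equal groups

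*Protocol*

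**What the plan says.** Four statements bear on which screened infants go on to full assessment.

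- Protocol, Method: "We will study all screen positive and a sample of screen negative infants". No limit is set on the screen positives.
- Protocol, Sample Selection, opening sentence: "Quota sampling will be used to obtain three equal groups of patients with different undernutrition scores (low, medium, high", continued "until the desirable number of patients in each group is achieved". No number per group is attached to the quota.
- Same section: high scorers, "expected to be only 10-20% of all patients", are to be oversampled "if necessary by screening all eligible patients using iPYMS and proceeding to full assessment for only those scoring high risk".
- Same section, introduced as a restatement of the previous rule: "The majority of patients screened at high risk of undernutrition", "Every third child screened at medium risk of undernutrition" and "Every tenth child screened at low risk of undernutrition".

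Subjects gives an average of 8 admissions a day and a target of 200 over 4 months. It mentions a possible second hospital without an inflow. The power section gives two equal-group scenarios: 45 per group for 0.66 SD at 90% power, and 70 per group for 0.5 SD at 80% power. Recruitment requires consent and a carer who reads English. It also says that most children go home on the first day, while assessment is planned for the day after admission.

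**The concern.** These are different instructions for one decision on the ward. A researcher with a high scorer in front of them cannot tell whether to take every such infant, most of them, or as many as the quota allows. With a medium or low scorer, they cannot tell whether the infant is sampled at a fixed fraction, taken until a quota is full, or not taken at all. The conditional high-risk-only step might pass as a late-stage fallback, but the text equates it with a list that includes medium and low scorers.

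Two things depend on this. The power statements assume equal groups. Sensitivity and specificity are aims of the study, and in a sample selected on the screening result they can be carried back to all screened infants only through the share assessed at each level. Those shares depend on the rule that was followed.

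**Working it through.** **Inputs.** From the protocol: 8 admissions a day, 4 months, total 200, three equal groups, high-risk share h of 10-20%, fractions 1/3 (medium) and 1/10 (low). Assumed: 4 months is 120-122 days, so A = 960-976 admissions; power is for a two-sided t-test at 0.05. Derived: 200/3 = 66.7, about 67 per group. The protocol gives no medium:low split.

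**The plan's own power figures.** 45 per group at 0.66 SD gives 87.2% (stated 90%). 70 per group at 0.5 SD gives 83.6% (stated 80%). Both are close enough for values read off a nomogram, and nothing below depends on the difference.

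**Clash between the rules.** All screen positives is A × h: 960 × 0.10 = 96 up to 976 × 0.20 = 195, if all are available. At 20% that alone nearly uses the total of 200. A quota of 66.7 would take 66.7/96 = 69% of high scorers at the low end and 66.7/195 = 34% at the high end. So the quota and the instruction to take most high scorers also part company within the stated range.

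**Do the fractions deliver equal groups?** With every admission screened and available and the fractions then applied, n medium infants need 3n at that level and n low infants need 10n. Together that is 13n infants who are not high risk, so total infants needed = 13n/(1 − h). This is the most favourable medium:low split; any other needs more.

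| h | Needed for 66.7 per group | Smaller group at best, A(1 − h)/13 |
|---|---|---|
| 10% | 963 | 66.5-67.6 |
| 15% | 1020 | 62.8-63.8 |
| 20% | 1083 | 59.1-60.1 |

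Against 960-976 admissions, no split works at 15% or 20%. At 10% with 976 admissions it works only if the medium share lies between 3 × 66.7/976 = 20.5% and 90% − 10 × 66.7/976 = 21.7%.

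**Size at the best split.** Power at 59 per group is 76.8% (0.5 SD) and 94.5% (0.66 SD). At 64 per group it is 80.1% and 96.0%. At 67 per group it would be 81.9% and 96.7%. Extra time to reach 66.7: 1020/8 = 127 days at 15% and 1083/8 = 135 days at 20%, against 120-122, so roughly one to two weeks.

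**With losses (assumed).** Take 75% of 976 as available (732), a medium share of 20-30%, and groups capped at 67.

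- Medium: 732 × 0.20/3 = 49, up to the cap of 67.
- Low: 732 × 0.50/10 = 37 to 732 × 0.70/10 = 51.
- High: at least 732 × 0.10 = 73, so capped at 67.
- Power, medium versus low: 66-73% (0.5 SD) and 88-92% (0.66 SD).
- Power, high versus low (hypothesis 2): 67-76% and 89-94%.

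**The case against.** Much of the wording has a workable reading. The quota governs, the Method sentence is a general summary, and the high-risk-only step applies once the other groups are full. That is probably the intention, and the fix adopts it. What it cannot absorb is the literal difference between all and most high scorers, or the phrase that equates a high-risk-only step with a list covering all three levels.

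The shortfall from the fractions alone is small. A reader might infer that the study cannot reach adequate numbers, and the documents do not support that. At the best split the smaller group stays well above the 45 of the first power scenario, and 64 per group still gives 80% at 0.5 SD. The 4 months is an aim and not a hard stop. The possible second hospital could close the gap: if the 8 a day refers to the main site only, about 0.4 to 0.9 more admissions a day over 122 days would be enough, from (1020 − 976)/122 and (1083 − 976)/122. The larger losses rest on an availability and a medium share that the protocol does not give. Losses from consent, language and discharge would also affect any selection rule.

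A reader might also infer that sensitivity and specificity can no longer be carried back to all screened infants. That goes too far. The iPYMS sheet is completed for each child, so if screened and assessed counts are kept per level, the realised fractions can be calculated whichever reading was followed. Finally, 45 per group is a power scenario, and should not be read as a minimum the protocol has set.

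**Conclusion.** The point stands, mainly on the wording. Method and Sample Selection give rules that cannot all be applied, and the ward researcher has no stated quota number to settle which prevails. Second, and smaller, the fixed fractions do not reliably produce the equal groups. At 15-20% high risk the smaller of the medium and low groups falls short of 67 at every split. At 10% about 67 is just reachable at around 21% medium, so the shortfall does not hold across the whole stated range. Only one of the two groups need be short.

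The best-case result rests on 120-122 days, every admission being screened and available, and no contribution from a second site. The 67 is derived, and two-sided 0.05 is assumed. The wider losses (37-51 low, 49-67 medium) illustrate what 75% availability with 20-30% medium would do; they are not predictions. The protocol should be corrected, but the design is not undermined.

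**What to change.** State one rule and use it in both sections.

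- **Sample Selection:** the quota per iPYMS level governs, about 67 each and 200 in total. Each level closes when full, and high scorers are taken consecutively until then. One in three and one in ten are starting fractions that may be raised, with the date recorded, if the medium or low group is falling behind. Confine the high-risk-only step to the stage when the other two quotas are full, and drop the phrase that equates it with the three-level list.
- **Method:** replace the unlimited inclusion of screen positives with screen-positive infants taken consecutively until their quota is full.
- **Records:** keep counts of infants screened, available and assessed at each level, by period of constant fraction, so that sensitivity and specificity can be weighted back to all screened infants.

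How and when a fraction is raised can be left to the study team, provided each change is dated. The cost is a change of wording and a running tally from the iPYMS sheets; the total stays at 200. The drawback is that sampling fractions may vary over time and must be tracked for the weighting. Raising a fraction also cannot fill a level that has too few available infants.

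### Low- and medium-risk infants enter full assessment by a predictable count run by the researcher who also scores iPYMS, so selection can be steered; a concealed random draw at the same fractions would prevent foreknowledge

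*Protocol*

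**What the plan says.** **Selection rule.** Under Sample Selection the Protocol states "Quota sampling will be used to obtain three equal groups of patients with different undernutrition scores (low, medium, high"), continuing until each group has enough infants. The same section then gives a count for the two lower bands, "Every third child screened at medium risk of undernutrition. c) Every tenth child screened at low risk of undernutrition", and for the top band "The majority of patients screened at high risk of undernutrition". It also allows, if needed, "screening all eligible patients using iPYMS and proceeding to full assessment for only those scoring high risk". The Method section says instead that every screen-positive infant and a sample of screen-negative infants will be studied.

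**Who does what.** Recruitment: "The researcher will identify those patients eligible for screening by visiting the wards daily and obtaining details of new admissions from the nursing staff". The same researcher gives out the leaflet and returns for consent. The section on development of iPYMS: "On admission this tool would be completed by the nurse (researcher initially"). Method: "The researcher will first complete the iPYMS scoring sheet for each" child. Outcome Measurements: the researcher also takes the skinfolds.

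**How the score forms the groups.** "A score of 0 or 1 classify patient at a low and median risk of undernutrition and a score of 2 or more" is high risk. One of the four items, poor weight gain, rests on parental report.

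**What is not described.** There is no random start, fixed screening order, concealed list, independent keeper of the count, log of all screened infants, or rule for selected infants who refuse or go home.

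**The concern.** After nine low-risk infants have been passed over, whoever keeps the count knows that the next one will be taken; the same holds after two medium-risk infants. Here that person also decides the order in which infants are approached, sees them, and settles borderline items. A single point moves an infant from a 1 in 10 chance of full assessment to 1 in 3, or from 1 in 3 to nearly certain. The steering need not be deliberate.

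Hypothesis 2 compares fat levels between score groups, and the false-negative proportion (Analysis-Statistics) depends on which low- and medium-score infants are examined. If thriving or easily measured infants were preferred in the low-risk group, the skinfold gap would widen and fewer missed cases would be found. A preference for lean infants would do the reverse. If steering did occur, the true selection probabilities would no longer be 1/3 and 1/10, and reweighting by those fractions would not repair the estimates.

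**Working it through.** **1. The Protocol's own figures.** With SD 1 and two-sided alpha 0.05 (assumed; neither alpha nor sidedness is stated), power ≈ Φ(d/√(2/n) − 1.96).
- n = 45, d = 0.66: Φ(3.13 − 1.96) = 87.9%, against 90% stated.
- n = 70, d = 0.5: Φ(2.96 − 1.96) = 84.1%, against 80% stated.

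The gaps are small, fit rough nomogram reading, and do not bear on this point. The target of 200 gives 200/3 ≈ 67 per group.

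**2. Can the count and the equal quotas both hold?** Filling 67 places at 1/10 and 1/3 needs 67 × 10 = 670 low-risk and 67 × 3 = 201 medium-risk infants screened, 871 together. Eight admissions a day for about 120 days (my reading of 4 months) gives 960. The Protocol expects 10-20% to be high risk, which leaves 768 to 864 low and medium infants. On these figures the strict count falls slightly short of three equal groups even before exclusions, refusals and early discharges. One rule would have to give way, and the Protocol does not say which.

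**3. What a shift would do (illustration, not an estimate).** Suppose steering moves the low-risk mean by b SD and there is no true difference. With SE = √(1/n₁ + 1/n₂), the two-sided rejection rate is Φ(b/SE − 1.96) + Φ(−b/SE − 1.96).

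| b (SD) | 67 v 67 (SE 0.173) | 58 v 67 (SE 0.179) | 38 v 67 (SE 0.203) |
|---|---|---|---|
| 0 | 5.0% | 5.0% | 5.0% |
| 0.05 | 6.0% | 5.9% | 5.7% |
| 0.10 | 8.9% | 8.6% | 7.8% |
| 0.20 | 21.2% | 20.0% | 16.6% |
| 0.25 | 30.4% | 28.6% | 23.4% |

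For 67 v 67 and b = 0.10: b/SE = 0.579, so Φ(−1.381) + Φ(−2.539) = 0.0836 + 0.0056 = 8.9%. A shift of 0.05 to 0.25 SD is 10% to 50% of the 0.5 SD design difference.

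**4. Where such a b could come from.** If a share f of low-risk places goes to infants whose skinfolds lie s SD above those of a fair sample, b = f × s. For example, f = 10% and s = 0.5 give 0.05; f = 50% and s = 0.5 give 0.25. Neither f nor s is in the Protocol.

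**5. Group size under a random draw.** If 40-60% of 960 are low risk (assumed), 384 to 576 are screened. Independent draws at 1/10 select 38 to 58 on average, with SD √(384 × 0.1 × 0.9) = 5.9 to √(576 × 0.1 × 0.9) = 7.2.

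**The case against.** The strongest reply is that nothing is being allocated. The score defines the group, and taking every kth infant within a score band is a recognised systematic sample with known fractions. Kept strictly on consecutive admissions, it would be roughly representative. The Protocol names all new admissions to the chosen wards as participants and has daily visits, so if everyone is scored the discretion is mainly over order, and that order would have to be arranged before scores are known. This stands. It makes the bias a possibility and not a consequence of the rule. It does not remove the exposure, because no consecutive order is laid down, the infants are visible before scoring, and the scorer holds the count.

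Three stronger readings are tempting and are not supported:
- *That the plan favours iPYMS.* Steering could go either way or cancel out.
- *That the quota permits convenient replacements.* No replacement rule of any kind is written; this could only be inferred from the word quota.
- *That the false-positive rate will be 6-30%.* The shifts behind those figures are assumed. Because weight centile is already in the score, appearance may say less about skinfolds within a band than one would expect.

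That concealment is absent is itself inferred from the Protocol's silence.

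**Conclusion.** The point holds as a weakness in how participants are sampled for a validation study. It is not a failure of treatment allocation. The Protocol fixes a predictable selection rule and places it with the same role that orders the approaches, scores the infants and measures the outcome. Bias in the skinfold contrast and the false-negative proportion is therefore possible, mainly through the low- and medium-risk groups. The high-risk group is less exposed, although taking only a majority leaves some discretion there too.

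Size and direction cannot be derived from the Protocol. The 6-30% range is conditional on an assumed shift of 0.05-0.25 SD, SD 1, a two-sided 5% test and about 67 per group; it is lower with the 38 to 58 low-risk infants that the 1/10 fraction might yield. The change is worth making because it is cheap and makes the selection probabilities known.

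**What to change.** 1. Keep the 1/3 and 1/10 fractions, but replace the count with independent random draws for each score band. A team member who does not screen generates them in advance. They are revealed, for example by sequential sealed envelopes, only after the iPYMS sheet is completed and signed. Envelopes suit the paper scoring sheet; the Protocol describes no electronic system that could lock scores.
2. Screen consecutive admissions from the daily ward list and log every infant screened, with score and draw.
3. Record selected infants who refuse or are discharged as selected non-participants, do not substitute for them, and continue down the list. A substitute would alter the 1/3 and 1/10 probabilities.
4. Reconcile the selection rules: all screen-positive infants (Method) against three equal quotas, full assessment of high risk only, and majority/third/tenth (Sample Selection). State whether equal groups or the fractions take precedence.

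**Cost.** A short amendment and a few hundred prepared envelopes, with no extra staff or visits. Group sizes will vary by chance (SD about 6-7 in the low-risk group if 384-576 low-risk infants are screened, an assumption), and uncompensated refusals and early discharges will reduce them further.

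**What remains.** The researcher will still know that a higher score carries a higher chance of selection, though not the result of the next draw. Skinfolds measured by someone aware of the score are a separate weakness that this change does not remove.
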